8.3.3	Potential Benefits of Study Participation	18
8.3.4	Risk-Benefit Assessment	19
8.4	RECRUITMENT STRATEGY	19
8.5	INFORMED CONSENT/ASSENT AND HIPAA AUTHORIZATION	19
8.5.1	Waiver of Consent	20
8.5.2	Waiver of Assent	20
8.5.3	Waiver of HIPAA Authorization	20
8.5.4	Waiver of Consent and HIPAA Authorization	21
8.6	PAYMENT TO SUBJECTS/FAMILIES	21
9	PUBLICATION	21
10	REFERENCES	22

ABBREVIATIONS AND DEFINITIONS OF TERMS

AE	Adverse event
ARDS	Acute respiratory distress syndrome
CART	Classification and regression tree
CHOP	Children's Hospital of Philadelphia
CRF	Case report form
ELISA	Enzyme Linked Immunosorbent Assay
HIPAA	Health Insurance Portability and Accountability Act
IRB	Institutional review board
LCA	Latent class analysis
PICU	Pediatric intensive care unit
PELOD	Pediatric logistic organ dysfunction score
PRISM-III	Pediatric risk of mortality-III
VPS	Virtual PICU System

ABSTRACT

Context: Acute respiratory distress syndrome (ARDS) is a heterogeneous syndrome of acute respiratory failure which affects 45,000 children in the United States annually. Heterogeneity has contributed to negative trials, as interventions useful in one sub-type may not be useful in another. Biomarkers have the potential to identify sub-phenotypes of pediatric ARDS which may benefit from targeted therapy.

Objectives: Our overall goal is to risk stratify pediatric ARDS patients and to identify sub-phenotypes with shared biology in order to appropriately target therapies in future trials. Specifically, we aim to:

Aim 1: Validate and refine PARDSEVERE, a published protein biomarker-based pediatric ARDS risk stratification tool

Aim 2: Stratify pediatric ARDS into sub-phenotypes using a known 100-gene expression-based classifier to group subjects according to shared underlying biology

Aim 3: Identify *de novo* sub-phenotypes in pediatric ARDS using biomarkers and whole genome transcriptomics of peripheral blood

Study Design:

This is a prospective, multicenter study upwards of 500 intubated children with ARDS, with planned blood collection within 24 hours of ARDS onset and subsequent measurement of plasma protein biomarkers and peripheral blood gene expression.

Setting/Participants:

We will enroll upwards of 500 intubated children with ARDS from 16 academic pediatric intensive care units in the United States.

Study Interventions and Measures:

We will measure pre-determined biomarkers with known or suspected association with ARDS severity or outcome. Simultaneously, we will measure gene expression of peripheral blood. Both plasma biomarkers and gene expression profiles will be analyzed using various machine learning techniques, including classification and regression tree, latent class analysis, and hierarchical clustering with the goal of identifying sub-phenotypes of ARDS. These sub-phenotypes will be examined for association with outcome (primary is 28-day mortality), and explicitly tested for variation in response to exogenous treatments (e.g., corticosteroids).

1 BACKGROUND INFORMATION AND RATIONALE

1.1 Introduction

Acute respiratory distress syndrome (ARDS) is common and deadly in children: ARDS is characterized by acute onset of diffuse bilateral pulmonary edema and severe hypoxemia not fully explained by cardiac dysfunction [1, 2]. Primarily defined for adults, ARDS affects 45,000 children in the United States annually [3], representing 10% of mechanically ventilated children in pediatric intensive care units (PICUs)[4], with a mortality rate of 20% in the United States and 30% worldwide [5-7]. There are no specific pharmacological therapies for adult [8-19] or pediatric [20-23] ARDS despite several trials, and supportive care with lung-protective ventilation [24] and fluid restriction [25] remains the mainstay of treatment. ARDS is a heterogeneous syndrome, with patients having distinct co-morbidities and inciting etiologies (pneumonia, non-pulmonary sepsis). This heterogeneity has contributed to negative trial results, as therapies effective in some patients are ineffective in others [26]. Methods to reduce heterogeneity, including sub-phenotyping using protein and mRNA biomarkers, have been proposed for improving patient selection for future clinical trials [27].

Studies are needed specifically in pediatric ARDS: In children, a lack of therapies is further compounded by uncertainty in management, as guidelines are typically extrapolated from adult ARDS, with uncertain applicability [28]. However, pediatric ARDS possesses a distinct epidemiology [29], outcomes [30], and pathobiology [31], necessitating studies specific to this population. We have published how the lower mortality rate in children necessitates alternative patient-centered outcomes for observational and interventional studies [32]. Additionally, as risk factors and co-morbidities differ from adult ARDS [29, 33, 34], studies specifically investigating the pathophysiologic changes leading to increased alveolar permeability in children are sorely needed, and are currently lacking. For example, pediatric ARDS spans birth to 18 years of age, encompassing different stages of lung development. Over 13% of children with ARDS have a history of prematurity [35] and are at high risk for impaired pulmonary vascular and parenchymal growth, which contributes to hypoxemia, cardiac dysfunction, organ failure, and outcomes in pediatric ARDS in a manner distinct from adult ARDS [36].

1.2 Relevant Literature and Data

Adult ARDS possesses distinct subtypes representing different pathophysiologic mechanisms: In adult ARDS, studies of biomarkers collected during clinical trials [37-39] have led to the discovery of endotypes, or sub-phenotypes with shared pathophysiologic, biomarker, or transcriptomic profiles [27]. Two distinct endotypes, dubbed “hypo-” and “hyperinflammatory” have consistently been discovered in 4 trials using latent class analysis (LCA), a form of cluster analysis. The hyper-inflammatory endotype was characterized by higher proportions of patients in shock, with sepsis, and higher levels of inflammatory biomarkers. Three biomarkers (interleukin-8 [IL-8], bicarbonate, and soluble tumor necrosis factor-1 [sTNFR1]) adequately discriminated the two endotypes. These

endotypes have clinical relevance, as they showed differential association with higher positive end-expiratory pressure (PEEP) [37], conservative fluid management [38], and to simvastatin [39], with benefits of these interventions only seen in the hyperinflammatory endotype. Additional work in adult ARDS has demonstrated different biomarker profiles between direct (primarily pulmonary) and indirect (primarily non-pulmonary) inciting etiologies, with elevated lung epithelial damage biomarkers seen in direct ARDS, and elevated endothelial biomarkers in indirect [40], suggesting that these may also represent endotypes. However, to date, there has not been demonstration of differential response to therapies based on stratification by direct or indirect ARDS biomarker profiles.

[figure not shown]
Pediatric ARDS possesses distinct subtypes representing different pathophysiological mechanisms: Investigations of whether clinically relevant endotypes exist in pediatric ARDS are in their infancy. Our group has demonstrated that infectious and non-infectious ARDS, defined using clinical variables, have different predictors of mortality [34], suggesting the possibility of distinct endotypes. Very recently, endotypes defined by differential circulating levels of matrix metalloproteinases (MMP) were reported in a separate, smaller cohort of pediatric ARDS, with higher mortality in the “hyperinflammatory” endotype [41]. However, this is the sole example of biomarker-based endotyping in pediatric ARDS, and requires replication in a larger, prospective cohort. Furthermore, these endotypes were defined solely using MMP pathway proteins, and it is unclear whether endotypes defined using a broader array of biomarkers would prove more informative.

Identification of endotypes allows for predictive enrichment in clinical trials: Identifying endotypes with common underlying biology is requisite for predictive enrichment – selection of subjects more likely to respond to trial interventions based on a biological mechanism [26, 27]. In adult ARDS, the association between mortality and higher PEEP, conservative fluid management, or simvastatin was only observed in the hyperinflammatory endotype [37-39], suggesting that future trials of these interventions, which had no mortality benefit in the parent trials enrolling heterogeneous ARDS, should be restricted to this responsive endotype. Pediatric ARDS, with its lower mortality rate and distinct etiologic and co-morbidity profile, requires its own endotyping strategy, and cannot *a priori* rely on adult evidence. In pediatric sepsis, [name] (a co-Investigator on this proposal) has designed a gene expression-based endotyping strategy which identified two distinct endotypes with differential expression of glucocorticoid receptor signaling genes and with divergent response to corticosteroids [42-44]. Whether pediatric ARDS possesses clinically relevant endotypes with differential response to therapies remains unknown, and is the key goal of Aims 2 and 3.

Protein biomarkers can stratify mortality risk and allow for prognostic enrichment in pediatric ARDS: In addition to predictive enrichment, biomarkers have also been proposed for prognostic enrichment – the selection of subjects more likely to have the outcome of interest to improve power to detect an effect of an intervention [26, 27]. We developed and published a biomarker-based risk prediction tool (PARDSEVERE) which stratifies pediatric ARDS into low-, medium-,

and high-risk for mortality in 152 subjects from a single center [45]. PARDSEVERE used age and three plasma biomarkers (IL-8, macrophage inflammatory protein 1- α [MIP1 α /CCL3], and heat shock 70kDa protein 1B [HSPA1B]), and discriminated non-survivors with an area under the receiver operating characteristic curve (AUROC) of 0.85, outperforming other severity of illness scores. The low-risk strata had mortality < 5%, while the high-risk strata had mortality > 30%. If validated in Aim 1, this strategy could be used to identify subjects who should be either excluded (low-risk subjects with low probability of improved mortality from intervention) or included (subjects with higher predicted mortality) in an interventional trial. Furthermore, risk stratification and predictive enrichment can be combined to further identify endotypes which may have differential responses to therapies (Figure 1).

Figure 1: Hypothetical example of combining biomarker-based risk stratification (using PARDSEVERE) with transcriptomic-based endotyping. This theoretical construct was used to identify children with sepsis who were more likely to benefit from corticosteroids (35).

Biomarker-based endotyping and risk stratification offers advantages over clinical variables: Clinical variables offer little detail about underlying pathophysiology. This is relevant when considering targeted therapies beyond supportive care. For example, we have shown that angiopoietin-2 (ANG2) and soluble receptor for advanced glycation end-products (sRAGE), markers of endothelial and lung epithelial dysfunction, respectively, are elevated in pediatric ARDS non-survivors [46], suggesting utility for prognostic enrichment as well as mechanistic implications. Therapies targeting the ANG2 [47] and RAGE pathways [48] are already in pre-clinical trials. Biomarker characterization of pediatric ARDS would allow restriction of trial subjects to those with evidence of dysregulated ANG2 or RAGE pathways, combining prognostic and predictive enrichment.

Our group has demonstrated advantages of biomarker-based prognostic and predictive enrichment over clinical variables alone. Recently, we showed how a positive response to inhaled nitric oxide (iNO), defined by an improvement in oxygenation of $\geq 20\%$, was associated with shorter ventilator duration in pediatric ARDS [49]. No clinical variables, including age, history of prematurity, vasopressor support, echocardiographic evidence of pulmonary hypertension, etiology of ARDS, or baseline oxygenation predicted oxygenation response to iNO. However, levels of ANG2, a biomarker of endothelial dysfunction, predicted a positive oxygenation response. Separately, we developed PARDSEVERE using classification and regression tree (CART) methodology [45]. We tested several clinical variables, including known predictors of mortality (oxygenation, organ failure, immunocompromised status, vasopressor support) for inclusion in the model. However, CART selected age plus three biomarkers (IL-8, MIP1 α , HSPA1B) as the final model. A possible explanation for this finding is that the mortality risk from

being immunocompromised were better explained using biomarkers, rather than a clinical designation of immune status. In both cases, we demonstrated how biomarker-based enrichment and risk stratification can add value above clinical variables alone.

1.3 Compliance Statement

This study will be conducted in full accordance all applicable Children's Hospital of Philadelphia Research Policies and Procedures and all applicable Federal and state laws and regulations including 45 CFR 46. All episodes of noncompliance will be documented.

The investigators will perform the study in accordance with this protocol, will obtain consent and assent, and will report unanticipated problems involving risks to subjects or others in accordance with The Children's Hospital of Philadelphia IRB Policies and Procedures and all federal requirements. Collection, recording, and reporting of data will be accurate and will ensure the privacy, health, and welfare of research subjects during and after the study.

2 STUDY OBJECTIVES

The proposed studies will establish the presence and clinical relevance of protein and mRNA biomarker-defined endotypes in pediatric ARDS. Additionally, the studies will validate a mortality risk stratification tool which can be developed to provide real-time prognostic enrichment in future trials. Successful completion of the Aims will significantly advance our understanding of pediatric ARDS, provide insight into underlying pathophysiology, and provide testable hypotheses on whether the association between specific treatments used in pediatric ARDS and outcomes differ by endotypes.

2.1 Primary Objective (or Aim)

This protocol has 3 specific Aims:

Aim 1: Validate and refine PARDSEVERE, a published protein biomarker-based pediatric ARDS risk stratification tool

Aim 2: Stratify pediatric ARDS into endotypes using a known 100-gene expression-based classifier to group subjects according to shared underlying biology

Aim 3: Identify *de novo* endotypes in pediatric ARDS using biomarkers and whole genome transcriptomics of peripheral blood

2.2 Secondary Objectives (or Aim)

[figure not shown]
The secondary objectives are to:

- Associate endotypes with 28-day mortality
 - Associate endotypes with duration of mechanical ventilation
 - Associate differential response of therapies (e.g., corticosteroids) dependent upon endotypes.
-

3 INVESTIGATIONAL PLAN

3.1 General Schema of Study Design

The proposal is a prospective observational cohort study of pediatric ARDS taking place at 16 centers in the United States. The study involves simultaneous collection of plasma (for measurement of circulating biomarkers) and RNA-stabilized whole blood (for microarrays) within 24 hours of ARDS onset in upwards of 500 children (Figure 2).

3.2 Study Duration, Enrollment and Number of Sites

The study will be funded for 5 years (anticipated start date of July 1, 2019 until June 30, 2024). We anticipate enrollment beginning January 1, 2020 and lasting until December 31, 2022 (3 years). We have budgeted ample time for start-up (6 months) and extension of enrollment (up to 2 years) in case of slower than expected enrollment. Sixteen US sites have expressed interest:

- Children's Hospital of Philadelphia (DCC and main site)
- Cincinnati Children's Hospital Medical Center (Cincinnati, OH)
- Nationwide Children's Hospital (Columbus, OH)
- Texas Children's Hospital (Houston, TX)
- Children's Hospital of Wisconsin (Milwaukee, WI)
- Akron Children's Hospital (Akron, OH)
- Nicklaus Children's Hospital (Miami, FL)
- Children's Mercy Hospital (Kansas City, MO)
- Penn State Hershey Children's Hospital (Hershey, PA)
- Cooperman Barnabas Medical Center (Livingston, NJ)
- Riley Children's at Indiana University Health (Indianapolis, IN)
- Columbia University Medical Center (New York, NY)
- Arkansas Children's Hospital (Little Rock, AR)
- Children's Healthcare of Atlanta (Atlanta, GA)

-
- Children's Hospital Colorado (Aurora, CO)
 - Washington University (St. Louis, MO)

3.3 Total Number of Study Sites/Total Number of Subjects Projected

3.3.1 Duration of Study Participation

The study duration per subject will be up to PICU discharge. Subject involvement will be limited to the single approach for consent, and a single blood draw, both within 24 hours of eligibility (i.e., ARDS onset). The subject will be followed until PICU discharge for collection of clinical data (mortality status, duration of ventilation, therapies used).

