4.2.2 Discharge

Subjects will be followed for duration of PICU stay until PICU discharge, death, or 90 days after enrollment. Data for the stay will be collected in the paper CRF and uploaded on-site to a web-based Redcap database.

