5 STUDY EVALUATIONS AND MEASUREMENTS

5.1 Screening and Monitoring Evaluations and Measurements

5.1.1 Medical Record Review

All clinical data will be generated at the discretion of the care team and attending physician. The following data will be abstracted from the medical chart (paper or electronic):

Category	Data to be Collected
Demographic	Date of birth, date of PICU admission/transfer, date of discharge, gender, race/ethnicity, weight, height
Medical history	Comorbid illnesses, lung injury diagnosis, organ failure score
Blood gas data	PaO ₂ , PaCO ₂ , pH
Ventilator data	Mode of ventilation, peak inflating pressure, mean airway pressure, positive end-expiratory pressure, compliance, dead space fraction
Laboratory data	White blood cell count, chemistries, lactate
Outcomes	Ventilator days, PICU survival
Vital Status	Alive or deceased at PICU discharge

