6 STATISTICAL CONSIDERATIONS

6.1 Primary Endpoint

The primary endpoint of Aim 1 is successful performance of the PARDSEVERE risk stratification tool to discriminate 28-day mortality in pediatric ARDS. The primary endpoint of Aim 2 is application of a known 100-gene classifier to test whether transcriptomic endotypes exist in pediatric ARDS. The endpoint of Aim 3 is generation of novel proteomic and transcriptomic endotypes.

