6.2 Secondary Endpoints

Secondary endpoints will include association of endotypes with mortality and ventilator-free days at 28 days.

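### Mortality and ventilator-free days are defined at day 28, but no day-28 status is planned for children discharged alive from the PICU before then

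*Combined protocol and SAP*

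**What the plan says.** The day-28 horizon appears in four places in the combined protocol and SAP. The Abstract (Study Interventions and Measures) plans to relate sub-phenotypes to "outcome (primary is 28-day mortality"). Section 6.1 states: "The primary endpoint of Aim 1 is successful performance of the PARDSEVERE risk stratification tool to discriminate 28-day mortality in pediatric ARDS". Section 6.2 lists "association of endotypes with mortality and ventilator-free days at 28 days". Section 6.4.2 assesses PARDSEVERE against 28-day mortality and calls it validated if sensitivity is at least 0.85 and specificity at least 0.65, each with a 95% CI no wider than 0.16.

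The collection window is set elsewhere. Section 3.3.1: "The study duration per subject will be up to PICU discharge", and "The subject will be followed until PICU discharge for collection of clinical data (mortality status, duration of ventilation, therapies used"). Section 4.2.2 follows subjects during the PICU stay "until PICU discharge, death, or 90 days after enrollment". The table in section 5.1.1 lists ventilator days and PICU survival as outcomes, and vital status as "Alive or deceased at PICU discharge". Section 8.1.1 names the inpatient chart as the data source.

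No section provides for a chart check after PICU discharge, a call to the family or a death-record search. None says how a child discharged alive before day 28 is to be classified.

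**The concern.** The endpoint and the collection window do not match. The protocol gives a median ventilation time of 9 days (section 3.4.2). It gives no PICU length of stay, but it is a fair inference that many survivors leave the PICU well before day 28. For them, the planned data hold neither vital status at day 28 nor any later return to invasive ventilation.

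Two results are exposed. In Aim 1, deaths form the denominator of sensitivity. An unrecorded death leaves that denominator and enters the denominator of specificity, as a false positive if the tool flagged the child and as a true negative if it did not. For the secondary endpoint, a child who dies or is re-intubated after PICU discharge is credited with ventilator-free days that did not occur.

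**Working it through.** **Endpoint against collection, by group of children**

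- Died in the PICU: recorded. Section 5.1.1 collects the discharge date and section 8.1 mentions dates of ARDS, so the death can be placed before or after day 28, provided the discharge date serves as the date of death.
- Still in the PICU at day 28: observed at day 28.
- Discharged alive from the PICU before day 28: no later status is planned. The gap is confined to this group.

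**How many children.** Inputs from section 6.5: 500 subjects, 16% mortality. 500 × (1 − 0.16) = 420. This is a ceiling, since it treats every survivor as discharged before day 28.

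**The plan's own precision figure.** Section 6.5 gives 454 subjects for a CI width of at most 0.16 at sensitivity 0.85 and 16% mortality. With a Wald interval:

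- deaths needed = 1.96² × 0.85 × 0.15 / 0.08² = 76.5
- subjects needed = 76.5 / 0.16 = 478

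This does not reproduce 454. At 454 there are 454 × 0.16 = 72.6 deaths and the width is 0.164, which meets 0.16 only after rounding to two decimals. The present point does not rest on that figure.

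**Illustration of precision.** Assumptions: the 16% is true 28-day mortality, all 500 are evaluable, and sensitivity is 0.85 among recorded deaths. Width = 2 × 1.96 × √(0.85 × 0.15 / deaths).

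- 500 × 0.16 = 80 deaths, all recorded: 0.156
- 4 unrecorded (5% of 80, assumed), 76 left: 0.161

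**Illustration of bias.** Same assumptions, with true sensitivity 0.85 and specificity 0.65. There are 80 × 0.85 = 68 true positives and 420 × 0.65 = 273 true negatives. Let m deaths go unrecorded, a fraction s of them flagged by PARDSEVERE:

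- apparent sensitivity = (68 − m·s) / (80 − m)
- apparent specificity = (273 + m·(1 − s)) / (420 + m)

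| m (assumed) | s (assumed) | Sensitivity | Specificity |
|---|---|---|---|
| 4 | 0.35 | 66.6/76 = 0.876 | 275.6/424 = 0.650 |
| 4 | 0.85 | 64.6/76 = 0.850 | 273.6/424 = 0.645 |
| 4 | 1 | 64/76 = 0.842 | 273/424 = 0.644 |
| 8 | 0.35 | 65.2/72 = 0.906 | 278.2/428 = 0.650 |
| 8 | 1 | 60/72 = 0.833 | 273/428 = 0.638 |

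The value s = 0.35 is the false-positive rate implied by a specificity of 0.65. Sensitivity is unbiased only if the unrecorded deaths are flagged at the same rate as the others.

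The CI width moves with the bias. For m = 4 it is 2 × 1.96 × √(0.876 × 0.124 / 76) = 0.148 when s = 0.35, and 2 × 1.96 × √(0.842 × 0.158 / 76) = 0.164 when s = 1. Unrecorded deaths can therefore make the tool look better and more precise, or worse and less precise.

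**The case against.** The strongest textual defence is the 90-day limit in section 4.2.2. It does not close the gap: the sentence limits follow-up to the PICU stay, so 90 days caps long stays and does not extend observation past discharge. The second defence is that the inpatient chart could show a ward death. That is true, so it would be too strong to say that day-28 status can never be known. But no field or procedure captures it.

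The objections to size carry more weight. The documents give no post-PICU death rate, and it may be small. They do not say whether the 16% was ascertained at day 28 or at PICU discharge. If it is PICU mortality, 80 deaths would still be recorded and the width would stay at 0.156. Nor would a width above 0.16 be specific to this gap. Section 6.5 allows for about 10% unevaluable subjects, and 500 × 0.90 × 0.16 = 72 deaths gives a width of 0.165 with no post-PICU deaths at all. Section 3.3.2 instead expects 500 evaluable for the plasma aims.

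A reader might also infer that the study would simply report PICU mortality under a 28-day label, or that the plan counts early discharges as alive. The documents support neither. Dated PICU deaths can be placed on either side of day 28, and no classification rule is written, although counting these children as alive is the likely default.

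**Conclusion.** The mismatch holds on the text alone and needs no outside figure. Under the plan as written, the primary outcome is not collected for children discharged alive from the PICU before day 28, and ventilator-free days share the gap. What the data can support is PICU death by day 28.

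The effect is unquantified. About 420 of 500 children is an upper bound on those exposed, and the number is lower in practice because children still in the PICU at day 28 are observed. The step from 0.156 to 0.161 with four unrecorded deaths shows only how little slack the 0.16 criterion has. It assumes that 16% is true 28-day mortality, that all 500 are evaluable and that sensitivity stays at 0.85. It would be wrong to conclude that Aim 1 will miss its criterion, or that any particular share of deaths will be lost. The planned data also cannot show that the share is negligible, which is reason enough to correct the collection plan.

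**What to change.** Amend sections 3.3.1, 4.2.2 and 5.1.1 so that chart review continues to day 28 from ARDS onset (the second qualifying OI or OSI) for every subject, regardless of PICU discharge. Then:

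- Add fields for date of death, vital status at day 28 with its source (or the date last known alive if the child has left hospital), and any return to invasive ventilation by day 28.
- Classify deaths after day 28 as day-28 survivors.
- For children sent home or transferred before day 28 with no later record, state the assumption that they are alive and ventilator-free at day 28. Report how many there are, and add a sensitivity analysis that varies the assumption.

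If collection is not extended, rename the outcome PICU mortality by day 28 throughout. Plain PICU mortality would not do, because it would also count PICU deaths between day 28 and the 90-day cap.

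The cost is a short extra chart look-up by the same coordinators, a few CRF fields, and a minor amendment with a check that consent covers the longer window. No visit or sample is added. Sites hold the list linking subject IDs to identifiers (section 8.1), so the look-up is feasible, but section 8.3.2 removes identifiers soon after data collection, so it should be done before then.
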